#### 8. SAMPLE SIZE JUSTIFICATION

The final analyses for primary safety and effectiveness endpoints will apply Bayesian methods and use a beta-binomial model .

The power calculations for the Bayesian adaptive design are presented in the simulation report Appendix B Table 6 (probability of success). Under the assumption of 65% success rate for primary effectiveness and 8% rate for primary safety, with 330 subjects, assuming 10-15% attrition rate, we will have more than 90% power for declaring success for each of the primary endpoints controlling the type-I error at 5%.

The total of 330 enrolled subjects includes 280 subjects who will be treated using STSF catheter with EPU and 50 subjects be treated using ST catheter with EPU. Approximately 30 subjects may be excluded or discontinued before receiving treatment assuming 10-15% attrition rate.

#### 9. STATISTICAL ANALYSIS METHODS

#### 9.1 General Conventions

In general, descriptive statistics will summarize all primary, secondary, and additional endpoints as appropriate. For continuous variables, number of subjects/events, mean, standard deviation, median, 25% percentile, 75% percentile, minimum, and maximum will be provided. For categorical variables, frequency and percentage will be presented for each category.

#### 9.2 Subject Disposition

Disposition of the study subjects are defined as the following.

- Enrolled Subjects: subjects who sign the informed consent.
- Excluded Subjects: subjects who do not have the STSF/ST catheter inserted or have the STSF/ST catheter inserted but do not undergo ablation with VISITAG SURPOINTTM Module. Subjects who have the STSF/ST catheter inserted but do not

undergo ablation with VISITAG SURPOINTTM Module will be followed for 12 months.

- Lost to Follow-up Subjects: subjects who are enrolled and have STSF/ST catheter inserted and undergo ablation with VISITAG SURPOINTTM Module, but contact is lost after most recent follow-up visit (despite 3 documented attempts).
- Withdrawn / Early Termination Subjects: subjects who withdraw consent for study participation or are withdrawn by the investigator or are terminated from the study prior to completion of all follow-up visits.
- Completed Subjects: enrolled subjects who completed the 12-month follow-up visit.

#### 9.3 Demographics and Baseline Characteristics

Subject demographics, medical history, AAD medical history and other baseline data will be summarized descriptively for all enrolled subjects as well as the safety and PP populations.

#### 9.4 Analysis of Primary Endpoints

The primary effictiveness endpoint is the proportion of patients that are free from primary effectiveness failure at Month 12. The failure modes are defined in the section 5.1.1. The effectiveness success rate at Month 12 will be compared against the performance goal of 50%. The final analyses will apply the Bayesian methods using a beta-binomial model. The analysis population for the primary effectiveness endpoint will be the per protocol (PP) population.

The primary safety endpoint is the proportion of patients that had Primary Adverse Event (PAE) within 7 days (PV stenosis and atrio-esophageal fistula may occur up to 3 months). The PAE rate will be compared against the performance goal of 14%. The final analyses will apply the Bayesian methods using a beta-binomial model. The analysis population for the primary safety endpoint will be the safety population.

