#### 4.1.2 Primary Safety Endpoint

The primary safety endpoint is the incidence of any primary adverse event occurring within 7 days following an AF ablation procedure (including the initial and repeat procedures) using the STSF/ST catheter with the EPU per protocol, except atrio-esophageal fistula and PV stenosis, which may also be considered as primary adverse events if occurring greater than seven (7) days post the ablation procedure .

Primary adverse events include the following conditions (refer to Table 6-1 Primary Adverse Events for detailed instructions for defining these adverse events):

- Death
- Atrio-esophageal fistula
- Cardiac Tamponade\*+/Perforation+
- Myocardial infarction (MI)
- Stroke / Cerebrovascular accident (CVA)†, ††
- Thromboembolism
- Transient Ischemic Attack
- Diaphragmatic paralysis

- Pneumothorax
- Heart block
- PV stenosis
- Pulmonary edema (Respiratory Insuffciency)
- Vagal Nerve Injury
- Pericarditis
- Major vascular access complication / bleeding
- \* Hemodynamic compromise or instability is defined as Systolic BP < 80 mm Hg.
- + Cardiac Tamponade/Perforation occurring within 30 days of the AF ablation process will be considered Primary AEs
- † Subjects with non-focal global encephalopathy will not be reported as a stroke without unequivocal evidence based upon neuroimaging studies.
- †† Modified Rankin score assessments should be made by certified individuals.

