## 6.2.1 Primary Adverse Event

A Primary AE is one of the following events occurring within seven (7) days following an AF ablation procedure with the STSF/ST catheter and VISITAG SURPOINTTM module with EPU, except atrio-esophageal fistula and PV stenosis, which may also be considered as primary adverse events if occurring greater than seven (7) days post the ablation procedure .

PRIMARY ADVERSE EVENT	DESCRIPTION / CRITERIA	
Death	Patient death directly related to the device or procedure and occurs at any time during or after the procedure.	
Atrio-Esophageal Fistula	Is defined as a connection between the atrium and the lumen of the esophagus. Evidence supporting this diagnosis includes documentation of esophagus erosion combined with evidence of a fistulous connection to the atrium such as air emboli, an embolic event, or direct observation at the time of surgical repair. A CT or MRI scan is the most common method of documentation of an atrio-esophageal fistula.	
Cardiac Tamponade*+/Perforation+	The development of a significant pericardial effusion during or within 30 days of undergoing an AF ablation procedure. A significant pericardial effusion is one which results in hemodynamic compromise, requires elective or urgent pericardiocentesis, or results in a 1 cm or more pericardial effusion as documented by echocardiography. Cardiac tamponade should also be classified as" early" or "late" depending on whether it is diagnosed during or following initial discharge from the hospital.	
Myocardial Infarction	
 
The presence of any one of the following criteria:
 
Detection of ECG changes indicative of new ischemia (new ST-T changes or new LBBB) which persists for more than 1 h
 
Development of a new pathological Q waves on an ECG, and
 
Imaging evidence of new loss of viable myocardium or new regional wall motion abnormality
 
	

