#### 7.9.4 Analysis of Primary Endpoints

The primary effectiveness endpoint is the proportion of patients that are free from primary effectiveness failure at Month 12. The failure modes are defined in the section 7.5.1.1. The effectiveness success rate at Month 12 will be compared against the performance goal of 50%.

The primary safety endpoint is the proportion of subjects who have any primary adverse events occurring within seven (7) days following an AF ablation procedure using study catheters with EPU, except atrio-esophageal fistula and PV stenosis, which may also be considered as primary adverse events if occurring within three (3) months post the ablation procedure. The PAE rate will be compared against the performance goal of 14%. The final analyses will apply the Bayesian methods using a beta-binomial model

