#### **5.1.2** Primary Safety Endpoint

The primary safety endpoint is the proportion of subjects with any primary adverse event (PAE) occurring within 7 days following an AF ablation procedure (including the initial and repeat procedures) using the STSF/ST catheter with EPU, except atrio-esophageal fistula and PV stenosis , which may also be considered as primary adverse events if occurring greater than 7 days post the ablation procedure. The PAE rate will be compared against the performance goal of 14%.

The final analyses for primary safety endpoint will apply Bayesian methods and use a beta-binomial model .

The hypotheses to be tested for this evaluation are:

$$H_0: q \ge 0.14$$
 vs.  $H_A: q < 0.14$ 

where q is the PAE rate.

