#### 9.4.2 Interim Analysis

Two interim analyses are planned. The first will occur once all subjects who are treated using STSF catheter with EPU have completed their 3 months follow-up. The second interim will occur when all subjects who are treated using STSF catheter with EPU have completed their 6 months follow-up. The planned interim analysis will be based on data collected only in subjects who are treated using STSF catheter with EPU. For the safety endpoint, among patients with more than 3 months of follow-up at the time of the interim analyses, any atrio-esophageal fistula and PV stenosis occurring post procedure will be deemed PAE.

At each interim analysis, the trial will declare early success if the predictive probability of success at the final analysis is greater than or equal to 99%. Early success will be declared at an interim if:

- 1. The safety objective has been met, and
- 2. The effectiveness endpoint has greater than or equal to 99% predictive probability of success.

The predictive probability is the probability of observing the success rate larger than 0.50 if the study continues to the end, given the observed data.

All of the subjects will be followed up to 12 months even after we claim success at interim look and submit the results in support of a premarket application. A final CSR will be submitted after all of the subjects complete their 12 months follow-up.

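### The primary safety endpoint has conflicting event windows: three for fistula and PV stenosis, and a 30-day tamponade/perforation rule that the analysis text omits

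*SAP*

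**What the plan says.** **Fistula and PV stenosis** have three wordings.

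1. No upper limit. Protocol 4.1.2 treats these as events "which may also be considered as primary adverse events if occurring greater than seven (7) days post the ablation procedure". Protocol 6.2.1 and 7.5.1.2 say the same, and SAP 5.1.2 has "which may also be considered as primary adverse events if occurring greater than 7 days post the ablation procedure".
2. Capped at 3 months. Protocol 7.9.4 has "which may also be considered as primary adverse events if occurring within three (3) months post the ablation procedure", and SAP 9.4 counts PAEs "within 7 days (PV stenosis and atrio-esophageal fistula may occur up to 3 months".
3. Interim rule. Among patients with more than 3 months of follow-up, "any atrio-esophageal fistula and PV stenosis occurring post procedure will be deemed PAE" (SAP 9.4.2; the same in Protocol 7.9.4.2). No cap is stated.

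**Tamponade/perforation.** The lead sentence of Protocol 6.2.1 reads "A Primary AE is one of the following events occurring within seven (7) days following an AF ablation procedure" and excepts only fistula and PV stenosis. The lead sentence of 4.1.2 does the same. Yet the 4.1.2 footnote says "Cardiac Tamponade/Perforation occurring within 30 days of the AF ablation process will be considered Primary AEs", the footnote to Table 6-1 repeats it, and the tamponade row of that table has "The development of a significant pericardial effusion during or within 30 days of undergoing an AF ablation procedure". Protocol 7.5.1.2 and 7.9.4, SAP 5.1.2 and 9.4, and the 12-month PAE secondary (synopsis, Protocol 4.2.2 and 7.5.2.2, SAP 5.2.2) all give 7 days without a tamponade exception.

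**Two smaller mismatches.** Table 6-1 counts a related death at any time, under the same 7-day lead sentence. The synopsis requires that the event be related to the device or procedure, a condition that Protocol 4.1.2 and SAP 5.1.2 do not state.

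The synopsis points to Table 6-1 for definitions and has the Clinical Events Committee (CEC) adjudicate this endpoint. No passage says which window the CEC applies. The methods appendix cited in Protocol 7.9.4.1 and SAP 9.4.1 was not available for this review.

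**The concern.** The PAE rate must beat 14% for the trial to succeed, and the safety objective must also be met before early success can be declared at an interim. The set of events that make up this rate should therefore be unambiguous.

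As written, the same subject can be classified in different ways:

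- A tamponade on days 8-30 is a primary event under Table 6-1. Someone working from the SAP alone would leave it out of both the tested rate and the 12-month rate.
- A PV stenosis at month 5 in an early-enrolled subject would count at an interim under SAP 9.4.2 but not in the final rate under SAP 9.4.

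If the narrower reading is used, the observed rate is lower than the rate of the endpoint the protocol defines, and the test against 14% becomes easier to pass.

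**Working it through.** **Inputs.** Safety passes if Pr(q < 0.14 | y, n) > 0.95 with a Beta(1, 1) prior (SAP 9.4.1). The planning PAE rate is 8%, with 330 enrolled, 10-15% attrition and about 30 lost before treatment (SAP 8). So n is 330 × 0.85 = 281, 330 × 0.90 = 297, or 330 − 30 = 300. The interims use only the 280 STSF subjects (SAP 9.4.2): 280 × 0.85 = 238 and 280 × 0.90 = 252. The interim text gives no numeric safety rule, so the same 0.95 threshold is assumed there.

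**Step 1: the limit.** The largest passing y is the largest for which the Beta(1 + y, 1 + n − y) distribution function at 0.14 exceeds 0.95. The last two columns are the binomial chance of landing exactly on that limit.

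| n | Largest passing y | Posterior at y | Posterior at y + 1 | P(Y = limit), true rate 8% | P(Y = limit), true rate 10% |
|---|---|---|---|---|---|
| 281 | 29 | 0.961 | 0.942 | 3.0% | 7.7% |
| 297 | 31 | 0.960 | 0.942 | 2.5% | 7.3% |
| 300 | 31 | 0.965 | 0.949 | 2.7% | 7.4% |
| 238 (interim) | 24 | 0.957 | 0.935 | 4.5% | 8.5% |
| 252 (interim) | 26 | 0.951 | 0.928 | 3.5% | 8.1% |

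One more counted subject at the limit reverses the safety result at every n.

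**Step 2: the plan's own power.** P(Y ≤ limit) at a true rate of 8%, fixed sample without interims, is 93.4% (n = 281), 94.6% (n = 297) and 94.0% (n = 300). The stated figure of more than 90% reproduces.

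**Step 3: effect on the test.** Suppose the rate under the full definition is exactly 14% and d percentage points of it go uncounted. The chance of passing is then P(Y ≤ limit) at 14% − d. The values of d are assumptions.

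| n | d = 0 | d = 0.1 | d = 0.5 | d = 1.0 |
|---|---|---|---|---|
| 297 | 4.2% | 4.6% | 6.9% | 10.8% |
| 300 | 3.6% | 4.0% | 6.0% | 9.6% |

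**Step 4: are those values of d plausible?** Protocol 1.3.1 reports tamponade at any time in 2/159 (1.258%) and 4/161 (2.484%) in two earlier contact-force catheter studies. If late tamponades make up all of d, the share of tamponades that must fall on days 8-30 is:

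- d = 0.1: 0.1/2.484 = 4% to 0.1/1.258 = 8%
- d = 0.5: 20% to 40%
- d = 1.0: 40% to 80%

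Fistula, at 0.04% in the same section, adds almost nothing.

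**Step 5: chance that the window chosen decides the result.** The narrow count can never exceed the full count. The chance that the narrow count passes and the full count fails is therefore P(Y ≤ limit at q − d) − P(Y ≤ limit at q). At q = 8%:

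- d = 0.1: 0.8%, 0.7% and 0.8% for n = 281, 297 and 300
- d = 0.5: 3.3%, 2.8% and 3.1%

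**Step 6: incomplete windows at interim 1.** The protocol counts a month as 30 days and allows ±7 days at month 3, so that visit may fall on day 83. For a repeat ablation on day 60, a 30-day window closes on day 90 and a 3-month window on day 150. Neither is complete by day 83, and SAP 9.4.1 imputes no safety data.

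**The case against.** The case for leniency has real content.

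- A footnote attached to one listed event reads naturally as a specific exception to the general sentence, and all three places that give a tamponade window agree on 30 days. The death row can be read in the same way.
- Apart from fistula and PV stenosis, neither the SAP nor Protocol section 7 lists the PAE components. Their content must come from Protocol 4.1.2 and Table 6-1, so silence on tamponade does not prove that the window was dropped.
- The open-ended and 3-month wordings can be read as a lower and an upper bound. The separate 12-month secondary fits that reading, since an open-ended primary would largely duplicate it. The interim condition of more than 3 months of follow-up can likewise be read as a maturity requirement that matches the cap.
- A late tamponade that is a serious adverse event would still appear in the tabulation for more than 7 to 30 days. The 12-month PAE rate is descriptive and cannot change the trial decision.
- The chance of landing on the limit is not the chance of a reversed decision, which also needs a late event. Step 5 shows how much smaller that chance is when few events are late.

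These points soften the conflict and limit its likely size, but they do not remove it. SAP 5.1.2 and 9.4 restate the window for the tested rate with no tamponade exception and no pointer to Table 6-1. The serious adverse event table does not feed the 14% test. No passage states the lower-and-upper-bound reading, and the interim rule still lacks the final analysis's cap.

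**Conclusion.** The concern holds and should be fixed. SAP 9.4, followed literally, leaves out events that the protocol defines as primary, in an endpoint that must be met for the trial to succeed. The interim and final rules for fistula and PV stenosis also do not match.

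The practical effect is probably modest. With 0.1 points uncounted, the chance of wrongly passing stays below 5% at both n in Step 3. It exceeds 5% at 0.5 points, which would need 20-40% of tamponades to fall on days 8-30, and nothing in the documents supports or excludes that share. The power claim is not undermined. What remains undefined is which events the 8% planning rate and the 14% goal refer to.

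These figures assume a fixed-sample final analysis and, for the interims, the final 0.95 threshold. The unsupplied appendix might settle some of the wording.

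**What to change.** Write one event-by-event table giving, for each PAE, its window, the procedure it runs from and whether relatedness is required. Cite it in the Protocol synopsis, 4.1.2, 4.2.2, 6.2.1, 7.5.1.2, 7.5.2.2, 7.9.4 and 7.9.4.2 and in SAP 5.1.2, 5.2.2, 9.4 and 9.4.2. Check the methods appendix against it. The table should:

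- carry the protocol's existing 30-day tamponade/perforation window into the analysis sections and the 12-month secondary;
- give fistula and PV stenosis one upper limit, chosen by the sponsor, that keeps the primary distinct from the 12-month secondary and applies at the interims and the final analysis;
- reconcile the death window and the relatedness condition;
- run the longer windows from initial and repeat procedures, as the 7-day rule already does;
- say how subjects with an incomplete window at interim 1 are counted, and which window the CEC applies.

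The sponsor is not blinded to individual or aggregated data (Protocol 7.3, SAP 3), so the limit should be fixed and dated before further review of outcome data.

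The cost is wording in both documents and a recheck of power. Adverse events are already collected through 12 months and PAEs already go to the CEC. The counted rate may rise slightly. Power stays at 90% or more until the counted true rate reaches about 8.35% (n = 281), 8.51% (n = 297) or 8.42% (n = 300), found by solving P(Y ≤ limit) = 0.90 for the rate.

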#### 9.4.1 Final Analysis

The primary goal of the trial is to demonstrate effectiveness and safety. For the trial to be successful, both endpoints must be statistically significant relative to their respective PG goals.

The effectiveness endpoint will be assessed by testing the hypotheses:

$$H_0$$
:  $Pr(p > 0.5|x, n) \le 0.97$  vs.  $H_A$ :  $Pr(p > 0.5|x, n) > 0.97$ 

where p is the responder rate, x is the observed number of patients that are failure-free through 12 months ("responders"), and n is the number of subjects in the PP population. If the posterior probability of the primary effectiveness endpoint meeting the 50% PG is greater than 97%, then we meet the threshold for primary effectiveness success.

We model the number of responders

$$X \sim \text{Binomial}(n, p)$$
,

We use a Beta (0.01, 0.01) prior distribution. This prior is centered at 50% and has an effective sample size of 0.02 observations.

Then the posterior distribution is

$$(p|x,n) \sim \text{Beta}(0.01 + x, 0.01 + n - x).$$

Subjects with missing data on the effectiveness endpoint will have their outcomes multiply imputed from a longitudinal model.

Similarly, the hypothesis test for the safety endpoint is:

$$H_0$$
:  $\Pr(q < 0.14|y, n) \le 0.95$  vs.  $H_A$ :  $\Pr(q < 0.14|y, n) > 0.95$ 

where *q* is the PAE rate, y is the observed number of subjects who had PAE and n is the number of subjects in the safety population. If the posterior probability of the primary safety endpoint meeting the 14% PG is greater than 95%, then we meet the threshold for primary safety success.

We model the number of patients with PAE as

$$Y \sim \text{Binomial}(n, q)$$

with Beta(1, 1) prior distribution on q. No imputation for missing data will be performed for the safety endpoint.

The trial will be considered a success if BOTH

- 1. Pr(p > 0.5|x, n) > 0.97 AND
- 2. Pr(q < 0.14|y, n) > 0.95.

These thresholds control the overall Type I error rate for the trial below one-sided 5%. The Type I error for each endpoint individually is also below 5%. The protocol Appendix B contains a detailed description of the statistical methods planned for testing the hypotheses around the primary effectiveness and safety endpoints.

Note that the final analysis will be performed if early success is not declared at either of the two interim looks. If early success is declared at either of the two interim looks, a summary of the primary endpoints based on full 12-month follow-up will be provided. In addition, both safety

and effectiveness results will be descriptively summarized separately for patients treated with the ST and STSF catheters.

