#### 6. LEVEL OF SIGNIFICANCE

The type I error for the interim and final analyses of the primary endpoints is controlled at one-sided 5%.

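### The 0.95 safety threshold is applied at the STSF-only interims and again at the all-subject final, so safety type I error is about 6%, not below 5%

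*SAP*

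**What the plan says.** SAP section 6 makes the general commitment: "The type I error for the interim and final analyses of the primary endpoints is controlled at one-sided 5" per cent. Section 9.4.1 repeats it for the trial ("These thresholds control the overall Type I error rate for the trial below one-sided 5" per cent) and for each endpoint ("The Type I error for each endpoint individually is also below 5" per cent). Protocol sections 7.6 and 7.9.4.1 say the same.

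One safety criterion is defined, in SAP 9.4.1, with a Beta(1,1) prior: "If the posterior probability of the primary safety endpoint meeting the 14% PG is greater than 95" per cent, safety succeeds.

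SAP 9.4.2 sets two conditions for early success at an interim. The first is "The safety objective has been met, and" the second is a predictive probability of at least 99% for effectiveness. It gives no separate safety threshold for the interims. On who is analysed it says: "The planned interim analysis will be based on data collected only in subjects who are treated using STSF catheter with EPU". The final uses all subjects (SAP section 1), and section 9.4.1 adds that "the final analysis will be performed if early success is not declared at either of the two interim looks".

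**The concern.** Effectiveness is protected against repeated testing by a tightened final threshold (0.97) and a 99% predictive bar at the interims. Safety has neither. A device whose true PAE rate equals the 14% goal can pass on the STSF subjects at an interim or, failing that, on the STSF and ST subjects together at the end. Each of these tests uses close to the full 5% by itself. The two data sets overlap heavily but are not the same, so the chance of passing at least one exceeds the chance of passing either alone.

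Both endpoints must pass for trial success, but this does not protect safety when effectiveness is truly good. Safety then decides the outcome, and its two-look error becomes the trial's error. What is at stake is the error rate of the primary safety claim, in a study whose interim result is intended for a premarket submission (SAP 9.4.2).

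**Working it through.** **Inputs.**
- Null PAE rate 0.14, threshold 0.95 and Beta(1,1) prior: SAP 9.4 and 9.4.1.
- Enrolment of 280 STSF and 50 ST, attrition 10-15% or about 30 subjects, assumed PAE rate 8% and effectiveness 65%: SAP section 8.

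**Treated numbers, with attrition split in proportion.**
- 10%: 280 × 0.90 = 252 STSF and 50 × 0.90 = 45 ST, total 297.
- 15%: 280 × 0.85 = 238 STSF and 50 × 0.85 = 42.5, taken as 42 ST, total 280.
- 30 lost: 280 × 300/330 ≈ 255 STSF and 45 ST, total 300.
- None lost: 280 STSF and 50 ST, total 330.

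**Critical values.** For n subjects, c(n) is the largest y for which the Beta(1 + y, 1 + n − y) distribution function at 0.14 exceeds 0.95. For example, at n = 252 the posterior probability is 0.951 with 26 events and 0.928 with 27, so c = 26.

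**The plan's own figures first.** Counting only the final look, P(Y ≤ c(n)) at q = 0.14 is 4.3% (n = 280), 4.2% (297), 3.6% (300) and 4.1% (330). Safety power at an 8% PAE rate is 93.7%, 94.6%, 94.0% and 96.3%. Effectiveness power at 65% exceeds 99.9%, and its single-look error is 2.7-3.2%. So both the power statement and the below-5% statement reproduce at these sizes if the interim safety test is ignored.

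**Adding the interim test.** The interim passes if Y1 ≤ c(n1), with Y1 ~ Bin(n1, 0.14) in STSF subjects. Otherwise the final passes if Y1 + Y2 ≤ c(n2), with Y2 ~ Bin(n2 − n1, 0.14) in ST subjects. The two-look error is

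P(Y1 ≤ c(n1)) + Σ over y > c(n1) of P(Y1 = y) × P(Y2 ≤ c(n2) − y).

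The two interims contain the same STSF subjects and are counted as one safety look. Effectiveness is taken to qualify at an interim.

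| STSF, then all | c(n1), c(n2) | Interim alone | Added by the final | Either look |
|---|---|---|---|---|
| 252, 297 | 26, 31 | 5.12% | 1.09% | 6.21% |
| 238, 280 | 24, 29 | 4.52% | 1.36% | 5.89% |
| 255, 300 | 26, 31 | 4.41% | 0.98% | 5.39% |
| 280, 330 | 29, 35 | 4.33% | 1.30% | 5.63% |

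(The last column is rounded from unrounded terms.)

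Over every combination of 238-255 STSF and 42-45 ST subjects (72 in all), the error runs from 4.8% to 6.5% with a mean of 5.7%, and 96% of combinations exceed 5%. Over 238-280 STSF and 42-50 ST (387 combinations) the mean is 5.8%, the maximum 6.8%, and 97% exceed 5%.

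**How often effectiveness qualifies at an interim.** This was simulated with the SAP's piecewise exponential model and Gamma(1,1) priors, assuming uniform 12-month accrual and a constant hazard. At 65% effectiveness the 99% bar was met in about 73-75% of trials at the first interim and about 95% at the second. At 70% or more it was met in essentially all trials by the second. If the bar is met in 95% of trials, the 252/297 error is 6.1%.

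**The case against.** The strongest objection is that the interim safety rule has to be inferred. The 0.95 figure stands under the final analysis, while SAP 9.4.2 opens by requiring a 99% predictive probability of success at the final, and trial success means both endpoints. If that bar also covered safety, the error would be 4.2% (252/297), 4.4% (238/280), 3.6% (255/300) and 4.1% (280/330). However, the numbered conditions in 9.4.2 apply predictive probability to effectiveness only and ask that the safety objective already be met. The only safety objective defined is the 0.95 rule. Even under the other reading, about 11% of size combinations still exceed 5%, with a maximum of 5.1%.

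Second, the plan relies on a simulation appendix (B in the SAP, C in the protocol) that is not among the documents reviewed. It might set another interim threshold. If so, section 9.4.2 should state it, because an analyst working from the SAP would use 0.95.

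Third, the size of the excess depends on conditions, and this part stands. The result varies with the realised sample size because the counts are discrete, and a few combinations fall just under 5%. It also depends on effectiveness qualifying at an interim. If that happened in only half of trials, the four cases would give 4.5-5.2%; at 255/300 even 75% gives 4.95%. But type I error control has to hold across effectiveness rates, including good ones.

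The single-look error of 5.12% at n = 252 is a peak caused by discreteness. Over n = 238 to 330 the single-look error averages 4.3%, and 12% of sizes exceed 5%. The finding rests on the two looks together, not on that peak.

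**Conclusion.** The concern holds. As the rule is written, type I error for safety over the interim and final looks is 5.4-6.2% in the four planned-size cases and up to 6.5% over the 10-15% attrition range, against a stated value below 5%. The overall claim fails by the same amount when effectiveness is clearly met.

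This rests on four assumptions: 0.95 is the interim safety threshold; the interims use STSF subjects only; the two interims amount to one safety look; and effectiveness qualifies at an interim. Late events or repeat procedures between the two interims could shift the figures slightly. The excess is around one percentage point, but it contradicts an unqualified statement about the primary safety endpoint.

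**What to change.** Raise the safety threshold from 0.95 to 0.965 at every look in SAP 9.4.1 and protocol 7.9.4.1, and write it explicitly into the interim rule in SAP 9.4.2 and protocol 7.9.4.2. The two-look error becomes 4.2% (252/297), 3.9% (238/280), 4.4% (255/300) and 3.9% (280/330). Its maximum is 4.84% over the 72 combinations and 4.97% over the 387. A threshold of 0.96 clears the four cases but still exceeds 5% in 17-18% of combinations; 0.955 is not enough.

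The cost is some safety power at an 8% PAE rate and no extra subjects. Two-look power falls from 95.7% to 93.5% (252/297) and from 94.6% to 91.9% (238/280), and is at least 91.0% throughout, so the claim of more than 90% survives for the two-look design. Counted on the final look alone, power dips to 89.8% at the worst size, and the SAP should say which basis its power statement uses.

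If 0.95 is kept, restate the safety and overall type I error as about 6%, in SAP sections 6 and 9.4.1 and protocol 7.6 and 7.9.4.1. Either way, check the simulation appendix against the stated rule. Also reconcile the Protocol Summary, which times the interims on all subjects, with the STSF-only interims elsewhere. Testing the same subjects at every look would remove most of the excess.
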